6.5.5 Rescue medication

The Investigator will provide rescue medication (paracetamol, 20 x 500 mg tablets) to the patients at the baseline visit (visit 1).

Patients will be instructed to only take the rescue medication provided for pain in the injured area or any other pain (e.g., headache) or fever (e.g., due to common cold) they might experience during the study. One or two tablets may be taken, repeated after at least 4 hours, if needed, up to a maximum of 3000 mg per day. No rescue medication is allowed within 6 hours immediately preceding Visit 5 (72h).

The patient will receive a diary at Visit 1 to record the time and date that each dose of rescue medication is taken, the number of tablets taken and the reasons for the intake (for contusion-related pain or another reason). The patient will also assess spontaneous pain intensity immediately prior to each dose of rescue medication. At each visit, the Investigator or designee will review the diary. Empty packages and rescue medication not used will be shown to the Investigator or designee. The Investigator or designee will then compare the packages vs. the patient's record of rescue medication use and any discrepancies will be noted in the CRF. Further instruction, how to use the diary are highlighted in Chapter 6.5.8

The Investigator will further investigate any instances in which rescue medication was taken for reasons other than contusion and complete the Adverse Event Form, if appropriate.

6.5.6 Other concomitant treatment

Concomitant therapies prohibited during the study:

The following treatments may NOT be used after the start of study drug:

Use of systemic or topical NSAIDs, analgesics (other than paracetamol), opioids, corticosteroids (except for topical treatment of bronchial asthma), heparin, or psychotropic agents.

Concomitant therapies allowed during the study:

- \square Rescue medication (section 6.5.5) except for the 6 hours prior to visit 5 (72h).
- □ Application of standard care by rest, ice, compression (non-occlusive bandage), or elevation (RICE) can be considered at the discretion of the Investigator.

The Investigator will instruct the patient to notify the study center about any new medications and significant non-drug therapies (i.e. RICE) he/she takes after the start of the study drug. All medications and significant non-drug therapies taken during the 30 days prior to Visit 1 (0h,

Day 1) (including physical therapy and blood transfusions) or administered after the patient starts treatment with study drug must be listed on the Concomitant medications/Significant non- drug therapies CRF page. An AE CRF page should also be completed, if appropriate.

6.5.7 Patient card

To avoid the intake of non-permitted concomitant medication, it is important to inform other physicians who might treat the patient while participating in the study. Therefore, a card will be given to the patient at Visit 1 containing relevant information about his/her study participation, i.e., study medication, name and address of the Investigator with telephone numbers.

6.5.8 Diary

A diary will be handed out to the patient at Visit 1.

The patient has to fill in the diary in handwriting and provide the following information:

- □ Every time patch is applied the patient has to document the time and date of application.
- □ Every time rescue medication is taken (not allowed within 6 hours before Visit 5 (72h)), the patient has to document:
 - \Box The time and date of rescue.
 - □ The number of tablets taken.
 - □ The reason for rescue (blunt trauma pain/other).
 - □ If the pain is related to the blunt trauma, the spontaneous pain intensity prior to the intake on a VAS scale

The Investigator or designee will ensure that all diary entries completed by the patient are legible.

The Investigator or designee will review the diary at every visit and collect it at Visit 7 (Day 8 ± 2).

6.5.9 Study drug discontinuation and premature patient withdrawal

The study drug must be discontinued and the patient withdrawn from the study if the Investigator determines that continuing it would result in a significant safety risk for that patient. The following circumstances require study drug discontinuation:

- □ Withdrawal of informed consent
- □ Pregnancy
- □ Emergence of any clinically relevant serious adverse events
- Any other protocol deviation that results in a significant risk to the patient's safety

In addition to these requirements for study drug discontinuation, the Investigator should discontinue study drug for a given patient if, on balance, he/she thinks that continuation would be detrimental to the patient's well-being.

Patients may voluntarily withdraw from the study for any reason at any time. They may be considered withdrawn if they state an intention to withdraw, or fail to return for visits, or become lost to follow up for any other reason. If premature withdrawal occurs for any reason, the Investigator must determine the primary reason for a patient's premature withdrawal from the study and this information must be recorded on the Study Completion CRF.

Patients who are prematurely withdrawn from the study will not be replaced.

If a patient is discontinued or decides to withdraw from the study, all evaluations scheduled for the final visit will be performed within one week of study drug discontinuation. Every effort must be made to collect all the required data at the time of patient discontinuation. The Investigator or designee must complete the Study Drug Discontinuation, giving the date and primary reason for stopping the study drug.

For patients who are lost to follow-up (i.e. those patients whose status is unclear because they fail to appear for study visits without stating an intention to withdraw), the Investigator or designee should show "due diligence" by documenting in the source documents the steps taken to contact the patient, e.g. dates of telephone calls, registered letters, etc., in order to establish the reason for discontinuation and to check presence of any AEs.

6.5.10 Emergency unblinding of treatment assignment

An individual decoding unit containing emergency identification of the package will be provided with each treatment unit. These decoding units are not to be opened unless an actual medical emergency occurs. If the Investigator feels breaking the code is required, a Clinsearch representative should be consulted first, unless the delay would endanger the patient's health. The date, time the code was broken and reason for breaking the blind must be recorded. In the event that a decoding unit is opened, the Project Manager at Clinsearch and the monitor must be informed within 24 hours. The unblinded treatment code should not be recorded on the CRF.

It is the Investigator's responsibility to ensure that there is a procedure in place to allow access to the code break cards in case of emergency. The Investigator or designee will inform the patient who to contact in case of emergency when the investigator is unavailable. The protocol number, study drug name if available, patient number, and instructions for contacting the local Clinsearch affiliate (or any entity to which it has delegated responsibility for emergency code breaks) will be provided to the patient in case emergency unblinding is required at a time when the Investigator and backup are unavailable.

Study drug must be discontinued after emergency unblinding. Study drug also must be discontinued for any patient whose treatment code has been broken inadvertently or for any non-emergency reason.

6.5.11 Study completion and post-study treatment

No continuation supplies will be made available for the patients as no further treatment is expected to be necessary at the end of the study. However, if necessary, the Investigator will continue to treat the patient until the injury is resolved. Alternatively, the Investigator will inform the patient's general practitioner (GP) at the end of the study period and the patient will then be advised to visit his GP directly.

6.5.12 Early study termination

The study can be terminated at any time for any reason by the Sponsor, an IRB or a Health Authority. Such reasons may include, but are not limited to:

- change in the risk/benefit assessment due to unexpected findings related to the potential risk of the treatment,
- Detection of SUSARs that differ in severity, duration or frequency from the known safety profile
- Becoming aware of new evidence through publications or other clinical trials that would negatively impact the risk/benefit assessment

Should this be necessary, all patients should be seen as soon as possible and treated as described in section 7 for a prematurely withdrawn patient. The Investigator may be informed of additional procedures to be followed in order to assure that adequate consideration is given to the protection of the patient's best interest.

The Investigator will be responsible for informing the IRB/REB/IEC of the early termination of the study. In the EU CRMB (EU legal representative) and Clinsearch will be responsible for notifying IECs, local authorities and the German Competent Authority, of the early termination of the study.

7 Visit schedule and assessments

Visit 1 (0 hour, Day 1) - Randomization visit

- \Box Written informed consent (section 10.2).
- \Box Check inclusion/exclusion criteria (section 5.1).
- \Box Demographic data (section 7.2).
- □ Brief, general physical examination is performed including vital signs, weight and height. Urine dipstick pregnancy test (WOCBP and postmenopausal women who are not surgically sterile only) (section 7.6).
- □ Medical history (previous and concomitant diseases) (section 7.2).
- \Box Concomitant medication (section 6.5.6).
- □ Assessment of injury (size of traumatization and localization).
- □ Spontaneous pain intensity, pain at rest (PAR) (section 7.5.1)
- \Box Injury site pain-on-movement (POM) (section 7.5.1).
- \Box Eligible patients receive a randomization number (section 6.5.1).
- □ The Investigator or a study nurse/doctor's assistant applies the first dose of study drug at the study center. Record information on AEs that occur after treatment (section 8.1).
- \Box Dispense rescue medication and instruct the patient about appropriate use (section 6.5.5).

Visits 2 (12h \pm 1h), 3 (24h \pm 2h), 4 (48h \pm 4h)

These visits will entail the following procedures, except as noted:

- \Box Apply next dose of study medication.
- □ Count used/unused patches & collect used patches

Teikoku Chemical Co. Ltd Clinical Study Protocol : TK-254R-0201

Documentation of use of rescue medication, if needed (diary check).

- \square Record changes in the use of concomitant medication (section 6.5.6).
- \square Record information on AEs (section 8.1).
- \Box Spontaneous pain intensity, pain at rest (PAR) (section 7.5.1)
- \Box Injury site pain-on-movement (POM) (section 7.5.1).
- □ Visit 4: Global efficacy assessments (GEA) by patient and investigator (section 7.5.1).
- \Box Adhesive power of patch (section 7.5.1).
- □ Local tolerability assessment (except V2).

Visit 5 (72h \pm 4 h)

- \Box Apply next dose of study medication.
- □ Count used/unused patches & collect used patches.
- □ Check for last intake of rescue medication no later than 6 hours prior to Visit.
- □ Documentation of use of rescue medication
- \square Record changes in the use of concomitant medication (section 6.5.6).
- \square Record information on AEs (section 8.1).
- □ Spontaneous pain intensity, pain at rest (PAR) (section 7.5.1)
- \Box Injury site pain-on-movement (POM) (section 7.5.1).
- \Box Global efficacy assessments (GEA) by patient and investigator (section 7.5.1).
- Responder rate 1 (number of patients achieving 50% reduction from baseline in the VAS score for POM)
- \Box Adhesive power of patch (section 7.5.1).
- □ Local tolerability assessment.

Visit 6 (96h+4h)

- □ Apply next dose of study medication.
- □ Count used/unused patches and collect used patches.
- \Box Use of rescue medication.
- \square Record changes in the use of concomitant medication (section 6.5.6).
- \square Record information on AEs (section 8.1).
- \Box Spontaneous pain intensity, pain at rest (PAR) (section 7.5.1).
- \Box Injury site pain-on-movement (POM) (section 7.5.1).

- \Box Adhesive power of patch (section 7.5.1).
- □ Local tolerability assessment.
- □ Dispense patient card (section 6.5.7) and diary (section 6.5.8) and instruct patient about appropriate use.
- Dispense three patches to the patient.
- \Box The patient is instructed on the method and time of application of study drug (section 6.5.4).

Visit 7 (Day 8 ± 2 days) - Final visit

Procedures for this visit are also to be completed if the patient terminates the study prematurely.

- \Box Count used/unused patches and collect used patches.
- \square Record changes in the use of concomitant medication (section 6.5.6).
- \Box Record information on AEs (section 8.1).
- □ Spontaneous pain intensity, pain at rest (PAR) (section 7.5.1)
- \Box Injury site pain-on-movement (POM) (section 7.5.1).
- \Box Global efficacy assessments (GEA) by patient and investigator (section 7.5.1).
- □ Responder rate 2 (number of patients able to resume training/ normal physical activity)
- \Box Adhesive power of patch (section 7.5.1)
- □ Local tolerability assessment.
- □ Collect remaining unused study drug and rescue medication.
- \Box Collect diary.
- □ Review diary
 - o Review the time and date of each patch application.
 - o Review rescue medication use. Count and document remaining rescue medication; (section 6.5.5).
- □ Perform a brief, general physical examination including vital signs and weight (section 7.6.1, 7.6.2). Urine dipstick pregnancy test (WOCBP and postmenopausal women who are not surgically sterile only) (section 7.6.4).
- \square Record changes in the use of concomitant medication (section 6.5.6).
- \Box Record information on AEs (section 8.1).
- □ Investigator evaluates whether the soft tissue injury/contusion has resolved and, if resolved, records the day and time it resolved.

Confidential Final Version 3.0

Table 7-1: Assessment schedule

8	Randomization visit (V1)	V2	V3	V4	V5	V6	Final visit ³ (V7)
Day	1	1 or 2	2	3	4	5	7, 8 or 9
Time after 1 st treatment	Oh	12h (±1)	24h (±2)	48h (±4)	72h (±4)	96h(±4)	7d (± 2d)
Written informed consent	X						
Inclusion / exclusion criteria	X						2
Demography / Med history	X						
Physical Exam / Vital Signs	X						X
Urine pregnancy test ¹	X						х
Concomitant medication	х	X	X	х	X	X	х
Injury site pain-at-rest (PAR)	X	X	X	х	X	X	х
Exam of soft tissue injury / contusion	х						х
Patch adhesion		X	X	Х	X	X	х
Local Tolerability assessment			X	х	X	X	х
Injury site pain-on-movement (POM)	х	x	x	x	x	x	х
Randomization	х						
Dispense IMP (patches) ²	х					x	
Dispense/Collect diary						X	х
Apply IMP (patch) at clinic	x		x	х	X	x	
Dispense rescue medication	X						
Count used/unused patches		X	X	х	X	X	х
Collect used IMP (patches)		x	x	x	x	x	х
Count rescue medication / Check time of intake		x	x	х	x	X	x
Adverse events		X	X	х	x	X	х
Global efficacy assessments				X	X		х
Collect rescue medication							X
Dispense three patches						X	
¹ Female patients only; ² Patients will be given pouch containing IMP to take home in case of need to replace a detached patch. Patients bring IMP with them to each subsequent clinic visit. Patient apply patches themselves at 120h and 144h. ³ A final visit will be							

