6.5.4 Instructions for prescribing and taking the study drug

All patients will be treated with 1 patch of study drug at every visit during the first 6 visits (except for visit 2). The first five patches will be applied at the study center. The site of the first application will be marked with a water-resistant pen to ensure the same application site at every treatment. Additional 3 patches will be dispensed at Visit 6. The patients will be instructed to apply one patch every day at approx. the same time. Dosing times should be distributed as evenly as possible, preferably once every 24 hours after the last application.

Patients can take a shower or bathe prior to the application.

The Investigator or study staff will instruct the patients to apply the study drug exactly as prescribed and state that compliance is necessary for the patients' safety and the validity of the study. The patients will be told to contact the Investigator or study staff if they are unable for any reason to apply the patch as prescribed. All dosages prescribed and dispensed to the patient

and all dose changes during the study must be recorded on the Dosage Administration Record CRF page.

If the hydrogel patch begins to peel-off (>10% of the total surface), the edges of the topical system may be pressed down. If problems with adhesion persist, patients may overlay the topical system with a mesh netting sleeve, where appropriate (e.g., to secure topical systems applied to ankles, knees, or elbows). The mesh netting sleeve must allow air to pass through and not be occlusive (non-breathable)

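### The section 7 procedure list for Visits 2 to 4 orders a patch application without excepting Visit 2, contradicting section 6.5.4, Table 7-1 and the once-daily regimen

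*Protocol*

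**What the plan says.** Protocol section 7 combines Visits 2, 3 and 4 under one heading and introduces the list with "These visits will entail the following procedures, except as noted". The first item is "Apply next dose of study medication" and the second is "Count used/unused patches & collect used patches". Further down, two items are limited to particular visits: the global efficacy assessment is labelled as a Visit 4 procedure, and the tolerability item reads "Local tolerability assessment (except V2", in parentheses. The dosing item has no such limit.

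Other parts of the protocol describe the dosing schedule differently:

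- **Section 6.5.4** gives one patch per visit "during the first 6 visits (except for visit 2", again in parentheses, and has the first five patches applied at the center. On spacing it says: "Dosing times should be distributed as evenly as possible, preferably once every 24 hours after the last application".
- **Table 7-1**, row "Apply IMP (patch) at clinic", is marked at Visits 1, 3, 4, 5 and 6 and is blank at Visit 2. Footnote 2 adds two home applications, at 120 h and 144 h, and lets patients take patches home to replace one that has come off.
- **Section 4** describes once-daily use with at most 7 patches, the first five doses being given at the site.
- **The synopsis** (Dosage) gives one patch once a day for 7 days.

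**The concern.** The list sets its own convention: every item applies at all three visits unless the item says otherwise. The dosing item says nothing, so by that convention it applies at Visit 2, and staff working through the list at 12 h are told to apply a patch. A site cannot follow both this instruction and section 6.5.4, and section 11 allows no agreed deviations.

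The stakes are limited but concern treatment itself. A site that followed the list would give an off-regimen patch before the 72 h primary assessment. A secondary matter is the compliance summary in protocol section 9.6 and SAP section 14.13, which divides by the number of scheduled applications. The schedule text should yield one number for that denominator.

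**Working it through.** **Inputs.** Nominal times are 0, 12, 24, 48, 72 and 96 h for Visits 1 to 6, with windows of ±1 h at Visit 2 and ±2 h at Visit 3 (protocol Tables 4-1 and 7-1). Home applications are at 120 h and 144 h (Table 7-1, footnote 2). The plan's own figures are five site doses and at most 7 patches (section 4). The cut for Good compliance is more than 80% of scheduled applications (SAP section 14.13).

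**Step 1: reproduce the plan's figure.** With Visit 2 excepted, site applications fall at 0, 24, 48, 72 and 96 h, which is 5. Adding 120 h and 144 h gives 5 + 2 = 7. Every gap is 24 h. This matches sections 4 and 6.5.4, Table 7-1 and the synopsis.

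**Step 2: count under the literal list.** Site applications fall at 0, 12, 24, 48, 72 and 96 h, which is 6. Adding the two home applications gives 6 + 2 = 8. The first two gaps become 12 h each and the rest stay at 24 h.

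**Step 3: patches applied before Visit 5 (72 h).**
- Intended: Visits 1, 3 and 4 = 3.
- Literal: Visits 1, 2, 3 and 4 = 4.

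**Step 4: early intervals with the visit windows.**
- Intended, Visit 1 to Visit 3: 24 ± 2 h = 22 to 26 h.
- Literal, Visit 1 to Visit 2: 12 ± 1 h = 11 to 13 h.
- Literal, Visit 2 to Visit 3: shortest 22 − 13 = 9 h, longest 26 − 11 = 15 h.

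**Step 5: compliance denominator (descriptive only).** Take a patient with six applications.
- Against 7 scheduled: 6/7 = 85.7%, above the 80% cut.
- Against 8 scheduled: 6/8 = 75.0%, below it.

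A patient given the 12 h patch as well as all 7 intended ones would show 8/7 = 114.3% of the intended schedule. The 8-application denominator is hypothetical: it would arise only if the list were taken to define the schedule.

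**Step 6: which text is wrong.** Section 6.5.4, Table 7-1, the synopsis and section 4 agree with one another. The tolerability exception in the same list points the same way, because the synopsis ties that assessment to what is seen at patch removal and also omits Visit 2. The unqualified dosing item stands alone.

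The Table 7-1 reading depends on columns recovered from a PDF, but section 6.5.4 says the same in prose and the count of five site doses confirms it.

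**The case against.** The best case against is that the correct instruction is hard to miss. Section 6.5.4 is the dedicated dosing section and names the exception outright. The table agrees, and on a once-daily regimen no next dose is due at 12 h. The opening phrase of the list could also be read to take in exceptions noted elsewhere. This shows that the intent is recoverable, which is accepted, but it does not make the list correct. Its exceptions are written on the items themselves, and the dosing item neither carries one nor refers to section 6.5.4.

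Four narrower points deserve weight:

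- **Compliance.** SAP section 3 refers to Table 7-1 for the schedule and SAP section 5.5.1 reproduces it, so 7 is the natural denominator. The compliance category is descriptive and is not named in the per-protocol definition. The 75.0% figure illustrates the ambiguity and does not predict a result.
- **The maximum of 7.** Replacement of a detached patch is allowed, and at Visit 6 the site is told "Dispense three patches to the patient" for only two home applications. The 7 is therefore better read as a count of scheduled applications than as a hard cap. The firm contradictions are with section 6.5.4, Table 7-1, once-daily dosing and the five site doses.
- **Collection at Visit 2.** The list and Table 7-1 both have used patches collected at Visit 2, which on its face suggests a patch change. Replacement of a detached patch can account for it.
- **Consequence.** The patch count at each visit would probably reveal an extra application. Randomization is stratified by center and center is a factor in the ANCOVA, so site-level misdosing would not confound the treatment comparison.

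These points limit the weight of the error. They do not remove it.

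**Conclusion.** The contradiction is real and the direction of the error is clear. Taken literally, section 7 gives 8 scheduled patches instead of 7, 6 site doses instead of 5, and 4 patches instead of 3 before the primary assessment, with a first interval of 11 to 13 h instead of 22 to 26 h. These are counts and intervals, not measures of drug exposure.

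The conclusion rests on reading the list by its own item-by-item convention. It does not assume that any site gave a 12 h patch, and the documents do not show that one did. Sample size, the primary analysis and the validity of the active-placebo comparison are unaffected. This is a minor to moderate correction that should be made because the line is an instruction on how to treat patients.

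**What to change.** In the Visits 2 to 4 list of protocol section 7, add *(except V2)* to the dosing item. Leave counting and collection of patches at Visit 2 unchanged.

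The cost is a qualifier on one line, made through the written amendment that section 11.1 requires, and a notice to three sites. Design, sample size and analysis do not change.

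SAP section 1 reports no protocol amendments. If enrollment has already ended, the equivalent step is to check the accountability records for applications at Visit 2, bring any to the blind review (SAP section 12), and fix the number of scheduled applications at 7 for the compliance summary.
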